**Table 2 Schedule of Assessments – Subjects in the Observational Cohort**

Study Period	Screening	Surgery			Follow-up Period						Unscheduled
		Visit Number	1	2 	3	4	5	8	9 	10/EoS 	
Day	-28	pre	peri 	post	2	3	4	7/DoD	30	90	
Visit Window	≥ -28 days	-	-	-	T0 + 24 hours	T0 + 48 hours	T0 + 72 hours	4 to 7 days	23 to 37 days	83 to 97 days	
Assessment											
Informed Consent	X										
Inclusion/exclusion criteria	X										
Medical history, demographics	X										
Medication use	X	X	X	X	X 						
Physical examination	X 										
Body weight, height	X										
Subject randomization											
Vital signs	X	X									
Hematology, biochemistry	X 	X 			X 	X 	X 	X 	X 	X 	
Urinary output 				X	X	X	X	X			O
Urinalysis	X 	X 						X 	X 	X 	X 
Pregnancy test	X 	X 									
NephroCheck®				X 	X 	X 	X 				
Biomarkers 		X		X	X 	X 	X 				
Assessment of AEs	X	X	X	X	X 						
Assess follow-up parameters											
Assess MAKE parameters					X	X	X	X	X	X	X
APACHE-II 		X		X							
EQ-5D-5L		X									
Blood samples for pharmacokinetics											
Blood samples for pharmacodynamics											
Biobanking sample PGx		X									

AE: adverse event; APACHE-II: acute physiology and chronic health evaluation II; DoD: day of discharge from hospital; EoS: end of study; EQ-5D-5L: 5-level European Quality of Life 5 Dimensions Questionnaire; MAKE: major adverse kidney events; O: if possible; PGx: pharmacogenomics; T0: time point 0; UO: urine output.

1. The preoperative period is defined as the part of the day of surgery before the incision. The peri-operative period is defined as the period between incision and T0 (i.e., the time point when the subject comes off the cardiopulmonary bypass pump [CPB]). The postoperative period is the period after T0.
2. During surgery, the following data have to be assessed in the electronic case report form (eCRF): Procedures (coronary artery bypass graft surgery and/or valve surgery, thoracic aortic surgery, extracorporeal membrane oxygenation, use of ventricular assist device, redo cardiac surgery) and duration of CPB; lowest intraoperative mean arterial pressure; perioperative fluid balance and medication (fluid intake, UO, blood products, drain output, blood loss, inotropics/vasopressors and furosemide); time of incision and closing of skin; T0 and perioperative complications.
3. Central laboratory tests
4. Additional urine samples will be taken and stored to assess various clinical and compound related biomarkers.
5. APACHE-II score is recorded on visit 2 preoperatively, postoperatively. Results from local laboratory testing can be used, and the result closest to the indicated time points should be recorded.
6. Visit 1 can be close to the day of surgery. If the results from the central laboratory testing of aspartate aminotransferase (AST), alanine aminotransferase (ALT), total bilirubin and eGFR are not yet available at time of randomization, results from local laboratory can be used for verifying randomization requirements if assessed within 7 days before the day of surgery up to initiation of surgery. When the surgery is scheduled within 2 days after screening visit 1 and it is not feasible to perform blood and/or urine samplings at visit 1, the sampling at visit 1 can be by-passed if the results from local laboratory are available for verifying randomization requirements.
7. Presurgery pregnancy test at the day of surgery will be assessed locally with urine dipstick test.
8. AEs and medication use will be collected until 24 hours after T0. However, AEs related to MAKE parameters will be collected until the EoS visit. AEs will be followed up until resolved including medication use for the AE.
9. Local laboratory test results will be collected from medical records, including serum creatinine and serum cystatin C (if available).
10. 24-hour urinary output data will be collected from medical records (if available).
11. Subjects will only be randomized if postoperative NephroCheck® (NC) AKIRisk® score (assessed between 2 to 22 hours after T0) is  $> 0.3 \text{ (ng/mL)}^2/1000$ . If the AKIRisk score is  $\leq 0.3 \text{ (ng/mL)}^2/1000$ , the subject cannot be randomized and will be followed up in the observational arm.
12. Urine sampling only for NC and biomarker assessments if subjects are still in the intensive care unit and urine can be sampled from the catheter. Urine samples will be taken, but frozen until later assessment at the central laboratory.
13. Visit 9 and 10 may be conducted by phone if the subject is unable to visit the site and will require contact for MAKE parameters collection.
14. When an assessment of a full physical examination is available and performed within 30 days before surgery, the assessment can be used even if it was performed prior to the informed consent.

### **3 STUDY OBJECTIVE(S) AND DESIGN**

#### **3.1 Study Objective(s)**

##### **3.1.1 Primary Objective**

- To evaluate the efficacy of postsurgery treatment with ASP1128 in subjects at risk for acute kidney injury (AKI) following CABG and/or valve surgery

##### **3.1.2 Secondary Objectives**

- To investigate the safety and tolerability of postsurgery treatment with ASP1128 in subjects at risk for AKI following CABG and/or valve surgery
- To investigate the pharmacokinetic characteristics of ASP1128 in subjects at risk for AKI following CABG and/or valve surgery

##### **3.1.3 Exploratory Objective**

- To investigate the pharmacodynamic characteristics of ASP1128 in subjects at risk for AKI following CABG and/or valve surgery
- To evaluate subject characteristics and biomarkers (including the NC device) for identifying subjects at risk for AKI following CABG and/or valve surgery

### **3.2 Study Design**

The study is a double-blind, placebo-controlled, randomized study with 1 ASP1128 and 1 placebo treatment arm. Randomization will occur in a 1:1 manner. There will be a cap on the proportion of subjects randomized with an estimated glomerular filtration rate (eGFR)  $< 45 \text{ mL/min per } 1.73 \text{ m}^2$  (assessed at visit 1 as per the Chronic Kidney Disease Epidemiology Collaboration [CKD-EPI] equation) of 20% of the total randomized. Randomization will be stratified for eGFR at visit 1  $< 45 \text{ mL/min per } 1.73 \text{ m}^2$ .

The eGFR will be calculated using the glomerular filtration rate (GFR) estimation equation in Kidney Disease Improving Global Outcomes (KDIGO) [KDIGO, 2013].

Gender	Serum Creatinine	Equation for Estimating GFR
Female	$\leq 0.7 \text{ mg/dl} (\leq 62 \text{ } \mu\text{mol/l})$	$144 \times (\text{SCr}/0.7)^{-0.329} \times 0.993^{\text{Age}} [\times 1.159 \text{ if black}]$
Female	$> 0.7 \text{ mg/dl} (> 62 \text{ } \mu\text{mol/l})$	$144 \times (\text{SCr}/0.7)^{-1.209} \times 0.993^{\text{Age}} [\times 1.159 \text{ if black}]$
Male	$\leq 0.9 \text{ mg/dl} (\leq 80 \text{ } \mu\text{mol/l})$	$141 \times (\text{SCr}/0.9)^{-0.411} \times 0.993^{\text{Age}} [\times 1.159 \text{ if black}]$
Male	$> 0.9 \text{ mg/dl} (> 80 \text{ } \mu\text{mol/l})$	$141 \times (\text{SCr}/0.9)^{-1.209} \times 0.993^{\text{Age}} [\times 1.159 \text{ if black}]$

GFR: glomerular filtration rate; SCr: serum creatinine

Source: [KDIGO, 2013]

The subject's age at visit 1 will be used for calculation of eGFR in this study.

Subjects are eligible for screening if they are scheduled for non-emergent (i.e., non-acute or directly life threatening) CABG and/or valve surgery within 4 weeks after screening.

Subjects cannot be rescreened once screening has failed.

Study visits include safety and efficacy assessments: chemistry, hematology and urinalysis laboratory assessments, UO, pregnancy test, physical examination, vital signs, blood pressure and assessment of AEs. In addition, blood and urine will be sampled for pharmacokinetics, pharmacodynamics, pharmacogenomics (PGx), metabolomics and biomarker assessments.

### **3.3 Randomization**

Subjects who have a NC AKIRisk score of  $> 0.3 \text{ (ng/ml)}^2/1000$  will be randomized in a 1:1 ratio to a treatment arm according to the randomization schedules through interactive response technology (IRT). There will be a cap on the proportion of subjects randomized with a eGFR  $< 45 \text{ mL/min per } 1.73 \text{ m}^2$  (assessed at visit 1 as per CKD-EPI equation) of 20% of total randomized. Randomization will also be stratified for eGFR  $< 45$  and  $\geq 45 \text{ mL/min per } 1.73 \text{ m}^2$  to allocate subjects equally between study groups within each stratification. The site personal will dispense the treatment according to the IRT system's assignment. Specific procedures for randomization through the IRT are contained in the study procedures manual.

Subjects with NC AKIRisk score of 0.3 or less will be enrolled in the observational cohort.

## **4 SAMPLE SIZE**

Sample size of this study is 220 randomized subjects (110 subjects in the ASP1128 group and 110 subjects in the placebo group).

The above sample size provides 80% power to detect the difference between ASP1128 and placebo on the primary endpoint of AKI proportion in the case of not considering an interim analysis, assuming the followings:

- AKI proportion in the placebo group is 60%
- Relative risk of ASP1128 against placebo is 0.7 (30% reduction)
- 1-sided significance level is 0.05
- Drop-out rate is around 10%

In addition, an interim analysis at 60% of enrollment as described below is planned by East® 6 software. Considering the interim analysis, the power is 78%.

- Futility stop criteria: conditional power to detect the relative difference between ASP1128 and placebo on the primary endpoint of AKI proportion is less than 10%, that is, 1-sided p-value is larger than 0.259, when approximately 60% of the planned acute kidney injury based on serum creatinine within 72 hours after Time point 0 (T0) (AKI-SCr72h) data have been collected in the study.
- There will be no provision to stop the study for efficacy in the interim analysis, so no efficacy stop criteria are defined.

Approximately 1000 subjects will be screened to enroll 600 subjects who meet the presurgery selection criteria. It is expected that 1 out of 3 subjects enrolled will meet the postsurgery criterion of having a NC AKIRisk score  $> 0.3 \text{ (ng/mL)}^2/1000$  and can be randomized: the

number of subjects to be randomized is 220. The subjects that have an AKIRisk score of  $\leq 0.3$  at the postsurgery 2- to 6-hour assessment will be enrolled in the observational cohort.

## **5 ANALYSIS SETS**

In accordance with International Conference on Harmonization (ICH) recommendations in guidelines E3 and E9, the following analysis sets will be used for the analyses.

Detailed criteria for analysis sets will be laid out in Classification Specifications and the allocation of subjects to analysis sets will be determined prior to database lock.

### **5.1 Full Analysis Set (FAS)**

The Full Analysis Set (FAS) will consist of all randomized subjects who receives at least 1 dose of study treatment (ASP1128 or placebo), and the analysis is based on the randomized treatment. This will be the primary analysis set for efficacy analyses.

### **5.2 Per Protocol Set (PPS)**

The Per-Protocol Set (PPS) includes all subjects of the FAS who do not meet criteria for exclusion from PPS listed in [Section 5.2.1] of this SAP.

The PPS will be a secondary analysis set for efficacy analyses. Select demographic and baseline characteristics may also be summarized for the PPS.

#### **5.2.1 Reasons for Exclusion From PPS**

The following reasons may lead to subject's exclusion from PPS:

1. Not complete scheduled three times administrations of study drugs
2. Administration of excluded concomitant treatment as described in the protocol
3. Violation of the any inclusion or exclusion criteria

### **5.3 Safety Analysis Set (SAF)**

The Safety Analysis Set (SAF) consists of all subjects who receives at least 1 dose of study treatment (ASP1128 or placebo), and will be used for safety analyses.

For the statistical summary of the safety data, the SAF will be used.

## **5.4 Pharmacokinetics Analysis Set (PKAS)**

The Pharmacokinetic Analysis Set (PKAS) consists of the subset of SAF for which at least 1 concentration available. Additional subjects may be excluded from the PKAS at the discretion of the pharmacokineticist.

The PKAS will be used for all summaries and analyses of the pharmacokinetic data.

## **5.5 Pharmacodynamic Analysis Set (PDAS)**

The Pharmacodynamic Analysis Set (PDAS) will include the subjects from the administered population for whom sufficient pharmacodynamic measurements were collected. The PDAS will be used for all analyses of pharmacodynamic data.

The PDAS will be used for all summaries and analyses of pharmacodynamic data.

## **5.6 Prognostic Factor Analysis Set (PFAS)**

The Prognostic Factor Analysis Set (PFAS) consists of NC positive subjects, who are randomized to placebo group, and the NC negative subjects, who are in the observational cohort.

The PFAS will be used for exploring the prognostic factors and comparison with to NC test.

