If the NC assessment is negative (AKIRisk score  $\leq 0.3$  (ng/mL) $^2/1000$  [at first and second measurements, if applicable]) or not assessable within the 2- to 6-hour window after T0, NC assessment may be repeated for up to 4 times within 22 hours after T0. Urine sampling should be done at intervals of at least 1 hour. If all the NC assessments are negative up to 22 hours after T0, the subject cannot be randomized and will be followed up in the observational cohort (see below).

Randomized subjects will receive 3 subsequent treatments with ASP1128 or matching placebo, which will be administered intravenously through a peripheral/central catheter. The first administration of study drug will occur after randomization, as soon as possible after the positive NC. If NC is positive in the initial 2 to 6 hours post T0 period, the first dose of IP should be completed within 8 hours after T0. If NC is positive in any of the additional NC measurements within 22 hours after T0, the first dose should be completed as soon as possible but within 24 hours after T0.

In case of reoperation on the day of surgery, the same time range for NC and drug administration applies in relation to T0 (i.e., NC between 2 and 22 hours and first investigational drug administration within 24 hours). A reoperation is no reason for not enrolling a subject as long as the NC can be performed at the described time points.

After surgery, UO will be monitored, safety assessments will be done and laboratory tests (including NC, SCr, cystatin C and other biomarkers) will be performed as per the Schedule of Assessments [Table 1].

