#### *Follow-up*

It is assumed that the subjects will be in the hospital up to at least 1 week after the surgery. On days 5, 6 and 7 after T0 (visits 6, 7 and 8, respectively) applicable assessments will be performed to assess study endpoints, including AKI (based on SCr). After end of all the procedures of visit 5, subjects can be discharged at the discretion of the investigator. If the subject is discharged before day 7, visit 8 will be done on the day of discharge and no site visits are required after discharge up to day 7. If the subject is discharged after day 7, visit 8 will be done on day 7 and no additional assessments are required after day 7 up to discharge, but the last result of SCr before discharge from local laboratory testing will be collected. Following day 7 (visit 8) or discharge, subjects will be followed up on day 30 (visit 9) and 90 (visit 10) following surgery. On visits 9 and 10, a composite endpoint of major adverse kidney events (MAKE) (all-cause mortality, renal replacement therapy [RRT] and/or  $\geq 25\%$  sustained reduction in eGFR) will be assessed.

Total number of hospital days and ICU days during initial hospitalization will be recorded. If the subjects are readmitted to hospital for any reason during the 90 follow-up days, the total number of hospitalizations and number of days hospitalized through day 30 and 90 will be recorded.

*Observational Cohort*

If at randomization NC is negative (AKIRisk score is  $\leq 0.3$  (ng/mL) $^2/1000$ ) at all assessments between 2 and 22 hours after T0, the subject cannot be randomized. These subjects will be included in the observational cohort. The rationale for following the subjects in the observational cohort is to further evaluate the AKIRisk score, as well as other risk factors (including clinical characteristics and biomarkers) for AKI and MAKE. The observational cohort will enroll a maximum of 440 subjects.

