### **Double-blind Treatment Period (Visits 2, 3, 4 and 5)**

#### Visit 2/Day of Surgery

Baseline assessments are performed before surgery on the day of surgery, including medication use between screening and day of surgery, safety laboratory tests, kidney function (eGFR, SCr and serum cystatin-C), biomarkers (e.g., kidney injury molecule-1 [KIM1], NC [see Section 5.4.2 Laboratory Assessments, [Table 7](#)]), vital signs and cardiac function (previous ejection fraction data from recent echocardiogram).

During surgery, various parameters will be recorded (e.g., incision time, CPB time, volume and type of blood products and infused fluids, UO and total blood loss). End of surgery for this study protocol is referred to as T0, which is defined as the time point when the subject comes off the CPB (i.e., the final separation from CPB and normal circulation is restored). This is thought to be the time point when the ischemia-reperfusion state starts that mediated the development of tubular damage and AKI. This time point is recorded by the perfusionist in the subject chart.

Four hours (with a range of 2 hours before and after) postsurgery (i.e., 2 to 6 hours after T0) a urine sample will be collected and the concentration of tissue inhibitor of metalloproteinase-2 (TIMP2) and insulin-like growth factor binding protein-7 (IGFBP7) will be assessed utilizing the NC device as per the package insert instructions. The urine sample should be fresh (i.e., not from accumulated urine in the bag so the bag should be emptied before the sample is taken); it can be obtained in the operating room/theater, recovery room or in the intensive care unit (ICU), as long as it is within the range of 2 to 6 hours post T0. For urine [TIMP-2] \*

[IGFBP7], a cutoff of 0.3 yielded good sensitivity and specificity at 4 hours after CPB [Meersch et al, 2014] and constituted an increased risk for developing AKI [Meersch et al, 2017]. The NC device will calculate the AKIRisk score. If NC is positive, i.e., the result of the AKIRisk score is  $> 0.3 \text{ (ng/ml)}^2/1000$ , the subject will be randomized and start treatment within 8 hours after T0 as per randomization schedule.

If the first result of the AKIRisk score is  $\leq 0.3 \text{ (ng/ml)}^2/1000$  the NC assessment should be redone once only if within the 2- to 6-hour window after T0 (i.e., the urine sample for NC should be taken within the 2 to 6 hours post T0 range).

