### I. The purpose of this amendment is:

| Substantial Changes                              |   |
|---|---|
| 1. Changes in Enrollment Numbers                 |   |
| DESCRIPTION OF CHANGE:                                  | The number of subjects to be enrolled in the observational cohort is changed to be capped at 440.   |
| RATIONALE:  | The current number of subjects in the observational cohort compared to the other cohort is higher than anticipated. The change is to cap the enrollment at the previously planned number. A higher number is not needed for the objectives of this cohort.  |
| 2. Changes in NephroCheck® (NC) Assessment       |   |
| DESCRIPTION OF CHANGE:                                  | The time window for post-surgical (coronary artery bypass graft and/or valve surgery) NC assessment is extended.  |
| RATIONALE:  | Review of the emerging data from the observation cohort showed a significant number of subjects had NC value > 0.3 after the current assessment window (i.e., 2 to 6 hours post-surgery). Based on available scientific literature and after confirmation with Key Opinion Leaders, NC increase within 24 hours after surgery is most likely due to an insult incited during surgery, and NC is approved to assess the acute kidney injury (AKI) risk in patients who have had acute cardiovascular compromise within the prior 24 hours. Extending the NC assessment window will identify subjects who have moderate or high risk for developing AKI, and therefore potentially be eligible for study treatment randomization. |
| 3. Addition of Details for Duration of Treatment |   |
| DESCRIPTION OF CHANGE:                                  | Parameters related to dosing of the investigational product are updated according to the extension of the NC assessment window.   |
| RATIONALE:  | The change is made to accommodate the extension of the NC assessment window. It is also expected that the wider treatment window after the surgery is supported to be effective based on preclinical data.  |

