#### ***Observational Cohort***

If at randomization NC is negative (AKIRisk score is  $\leq 0.3$  (ng/mL)/1000 at t = 4 hours [range 2 to 6 hours; at 1st and 2nd measurement, if applicable]), the subject cannot be randomized. These subjects will be included in the observational cohort. The rationale for following the randomization failures is to further evaluate the AKIRisk score, as well as other risk factors (including clinical characteristics and biomarkers) for AKI and MAKE.

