**Table 6 Demographic and Baseline Characteristics**

Item	Classification
Sex	1: Male 2: Female
Age (years) [Informed Consent]	Measurement value 1: < 65 2: >= 65
	1: < 70 2: >= 70
Ethnicity	1: Not Hispanic or Latino 2: Hispanic or Latino
Race	1: White 2: Black or African American 3: Asian 4: American Indian or Alaska Native 5: Native Hawaiian or Other Pacific Islander 6: Other
Height (cm) [Screening]	Measurement value
Weight (kg) [Screening]	Measurement value 1: < 60 2: >= 60
Tobacco History	0: Never 1: Current 2: Former
Alcohol History	0: Never 1: Current 2: Former
Drug Abuse	0: Never 1: Current 2: Former
Left Ventricular Ejection Fraction (%)	Measurement value 1: < 40 2: >= 40
AKIRisk Score ((ng/mL)  /1000) [Postsurgery] 	Measurement value 1: <= 0.3 2: > 0.3 to <= 0.7 3: > 0.7
eGFR for Randomization (mL/min/1.73 m  )	Measurement value 1: < 45 2: >= 45 1: < 60 2: >= 60
Peripheral Arterial Disease 	0: No 1: Yes
Use of Intravenous Radio-contrast 	0: No 1: Yes
Protocol Version Number at Enrollment	1: Before Version 2.0 2: Version 2.0 or Later

AKI: acute kidney injury; eGFR: estimated glomerular filtration rate

1: If AKIRisk Score at post surgery is recorded several times in eCRF, the last score will be used.

2: The record of “Are there any peripheral arterial diseases?” in Demographics eCRF will be used.

3: If subjects have at least one record in the Concomitant Medication eCRF with the flag selected “YES” for of use of Intravenous Radio-contrast between the date of screening and T0 of the date of surgery, then “Yes”; otherwise “No”.

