**Table 13 Potential Risk Factors for Development of AKI and MAKE**

Risk Factor	Classification
Circulatory Shock	0: No 1: Yes
Nephrotoxic Drugs	0: No 1: Yes
Radiocontrast Agents	0: No 1: Yes
Poisonous Plants and Animals	0: No 1: Yes
Dehydration or Volume Depletion	0: No 1: Yes
Advanced Age ( $\geq 70$ years)	0: No 1: Yes
Female Gender	0: No 1: Yes
Black Race	0: No 1: Yes
CKD	0: No 1: Yes
Chronic Diseases (Heart, Lung, Liver)	0: No 1: Yes
Diabetes Mellitus	0: No 1: Yes
Anemia	0: No 1: Yes
Prior AKI	0: No 1: Yes
Left Ventricular Ejection Fraction ( $<40\%$ )	0: No 1: Yes
AKIRisk Score ( $>0.3 \text{ (ng/mL)}^2/1000$ ) [Postsurgery]	0: No 1: Yes
AKIRisk Score ( $>0.7 \text{ (ng/mL)}^2/1000$ ) [Postsurgery]	0: No 1: Yes
Peripheral Arterial Disease	0: No 1: Yes
Use of Intravenous Radio-contrast	0: No 1: Yes
Higher Risk Surgery	0: No 1: Yes
Duration of CPB ( $\geq \text{Median}$ )	0: No 1: Yes
Duration of Aortic Cross-Clamp 1 ( $\geq 0.5$ hours)	0: No 1: Yes
Duration of Aortic Cross-Clamp 2 ( $\geq 1.0$ hours)	0: No 1: Yes
eGFR Based on Serum Creatinine ( $<45 \text{ mL/min/1.73 m}^2$ ) [Baseline]	0: No 1: Yes

CKD: chronic kidney disease; AKI: acute kidney injury; CPB: cardiopulmonary bypass pump; eGFR: estimated glomerular filtration rate

In addition to the above, the following analyses will be conducted for Observational Cohort.

- Primary efficacy endpoint and secondary efficacy endpoints will be summarized for the subjects with NC positive within T0 + 24 hours and NC negative within T0 + 24 hours and all subjects in Observational Cohort. In the table, each stage of AKI-SCr72h and AKI-SCr7d and each individual outcomes of MAKE30/90 will also be summarized.
- For Observational Cohort, the association between MAKE30/MAKE90 (and also each individual outcomes, of all-cause mortality, initiation of RRT and eGFR based on SCr at day 30 (Visit 9)/day 90 (Visit 10) equal to or less than 75% of the baseline value) and primary, secondary and exploratory endpoint of AKI proportion is evaluated by a contingency table. The following endpoints of AKI proportion will be used;
  - AKI-SCr72h (primary endpoint) and each stage,
  - AKI-SCr7d (secondary endpoint) and each stage,
  - AKI-SCr stage 2 or 3 (within 72 hours after T0), and
  - AKI-SCr stage 2 or 3 (within 7 days after T0)

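### The prognostic factor analysis pools NephroCheck labels from two testing rules (2–6 h before protocol Version 2.0, 2–22 h from it), so its accuracy figures describe neither rule

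*SAP*

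**What the plan says.** **The analysis.** SAP 5.6 defines the Prognostic Factor Analysis Set (PFAS) as "NC positive subjects, who are randomized to placebo group, and the NC negative subjects, who are in the observational cohort". SAP 7.9.1 then estimates a risk ratio, TPR and TNR for AKI-SCr72h, AKI-SCr7d, MAKE30 and MAKE90 for each factor in Table 13, on one weighted total. NC positives carry a single weight, all randomised subjects divided by placebo subjects, planned at 220/110 = 2. Table 13 has two AKIRisk rows (above 0.3 and above 0.7, postsurgery) and names neither a sampling window nor a protocol version. The SAP's rule for repeated scores is in Table 6, footnote 1: "If AKIRisk Score at post surgery is recorded several times in eCRF, the last score will be used".

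**The rule before Version 2.0.** The superseded synopsis text in Protocol Attachment 1 (Observational Cohort) classed a subject as NC negative on a score of 0.3 or less in the "range 2 to 6 hours; at 1st and 2nd measurement, if applicable". It is cited here only as the rule under which earlier subjects were classified.

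**The rule from Version 2.0.** The protocol synopsis says "NC assessment may be repeated for up to 4 times within 22 hours after T0". With a score of 0.3 or less "at all assessments between 2 and 22 hours after T0, the subject cannot be randomized".

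**Why it changed.** Attachment 1 says the emerging observational-cohort data "showed a significant number of subjects had NC value > 0.3 after the current assessment window". The same amendment capped that cohort at 440.

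**What the SAP already does.** Table 6, produced for the PFAS under SAP 7.2.3, counts protocol version at enrolment. SAP 7.9.1 also summarises outcomes in the observational cohort by NC status within T0 + 24 h. The revision history ties both additions to the Version 2.0 amendment.

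**The concern.** One of the trial's exploratory objectives is to evaluate NephroCheck for identifying subjects at risk of AKI. The TPR and TNR in SAP 7.9.1 are the figures that would answer it. They can be interpreted only if NC positive means the same thing for everyone in the denominator.

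It does not. Take a subject at or below 0.3 at 4 h and above 0.3 at 20 h. Before Version 2.0 that subject is an NC-negative member of the observational cohort. From Version 2.0, if the later repeat is done, the same subject is randomised as NC positive. The pooled figure averages an early-window rule and a positive-at-any-time-to-22-h rule, in proportions set by when the amendment took effect. A reader could apply the result to neither rule.

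**Working it through.** **Plan's own figure.** The plan states no figure for the PFAS analysis. Two planning inputs are borrowed from SAP Section 4: 1 in 3 subjects NC positive, written for the 2–6 h window, and 60% AKI on placebo. As a check that the 60% is read as the sponsor used it: 110 × 0.9 = 99 evaluable per arm, 60% versus 0.7 × 60% = 42%, one-sided 0.05, gives 81.7% power against the stated 80%. The point below does not depend on that calculation.

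**Classification by era**

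| Score profile | Before Version 2.0 | Version 2.0 or later |
|---|---|---|
| Above 0.3 at either test within 2–6 h | NC positive | NC positive |
| 0.3 or less within 2–6 h, above 0.3 later up to 22 h | NC negative | NC positive if repeated; NC negative if not |
| 0.3 or less throughout | NC negative | NC negative |

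Only the middle row, the late risers, changes label.

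**Size, as an illustration.** From the documents: 1/3 positive at 2–6 h, with 60% AKI. Assumed: 20% AKI in never-positives; a fraction f = 10–40% of early negatives rises by 22 h; AKI risk r = 30–60% in these; every late riser is caught under Version 2.0.

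Per 300 subjects there are 100 early positives (60 AKI), 200f late risers (200f·r AKI) and 200(1−f) never-positives (20% AKI). TPR = AKI labelled positive ÷ all AKI. TNR = non-AKI labelled negative ÷ all non-AKI.

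| f, r | TPR, 2–6 h | TPR, 2–22 h | TNR, 2–6 h | TNR, 2–22 h |
|---|---|---|---|---|
| 10%, 30% | 60/102 = 58.8% | 66/102 = 64.7% | 158/198 = 79.8% | 144/198 = 72.7% |
| 10%, 60% | 60/108 = 55.6% | 72/108 = 66.7% | 152/192 = 79.2% | 144/192 = 75.0% |
| 40%, 30% | 60/108 = 55.6% | 84/108 = 77.8% | 152/192 = 79.2% | 96/192 = 50.0% |
| 40%, 60% | 60/132 = 45.5% | 108/132 = 81.8% | 128/168 = 76.2% | 96/168 = 57.1% |

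The differences run from 5.9 to 36.4 points in TPR and from 4.2 to 29.2 points in TNR. The risk ratio is 1.67–2.86 under the 2–6 h rule and 2.33–3.00 under the 2–22 h rule. An equal mix of eras gives TPR 61–67%, TNR 65–77% and risk ratio 2.0–2.8.

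**Effect of the 440 cap.** Suppose the observational cohort fills in the first era, and an equal-sized second era then contributes NC positives only. With f = 10% and r = 60%:

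- First era: 60 true positives, 40 false positives, 48 false negatives, 152 true negatives.
- Second era: 72 true positives and 48 false positives.
- Pooled TPR = 132/180 = 73.3%. Pooled TNR = 152/240 = 63.3%.

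Both lie outside the span of the two rules (55.6–66.7% and 75.0–79.2%). A single overall NC-positive weight does not correct this.

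**The case against.** The best case against is that this is small and partly handled. The device and the 0.3 cutoff are unchanged. The old rule already allowed a second test within 2–6 h. Only late risers change label, and because later repeats are optional some remain NC negative under Version 2.0 too. The analysis is exploratory, with no hypothesis test or decision rule, and the AKIRisk score defines 2 of the 23 rows of Table 13. The sponsor plainly saw the era effect and added the version count and the T0 + 24 h split. All of this stands, and it limits the scope.

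It does not remove the point. The version count shows the mix but not the accuracy of either rule. The T0 + 24 h split stays within the observational cohort and gives no TPR or TNR. The frozen visit 3–5 urine in that cohort was collected only from subjects still in the ICU with a catheter (Protocol Table 2, footnote 12), so those samples cannot fully reclassify the earlier negatives. The version subgroups in SAP Table 12 serve the efficacy analysis on the FAS (SAP 7.4.3).

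A reader might infer more than the documents support:

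- **That a score near 22 h is concurrent with AKI, so not prognostic.** AKI-SCr72h uses creatinine at 24, 48 and 72 h (SAP 6.1.1), and the same analysis covers AKI-SCr7d, MAKE30 and MAKE90.
- **That late risers are known to be numerous.** The amendment gives no count and does not say how many were positive by 22 h.
- **That the pooled figure must lie between the two rules.** The cap example shows that it need not.

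**Conclusion.** The point holds for the exploratory NephroCheck analysis. The PFAS mixes subjects labelled under two testing rules, and the pooled TPR, TNR and risk ratio for the AKIRisk rows correspond to neither.

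The true size cannot be stated: the documents give neither the number of late risers nor the split of subjects by era. The spread of about 6–36 points in TPR and 4–29 points in TNR rests on the assumed 20% AKI in never-positives, the assumed share and risk of late risers, and complete capture of late risers under Version 2.0. Incomplete capture would shrink the gap. The cap effect also depends on when the cohort closed, which the documents do not say.

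The randomised comparison and the primary endpoint analysis are not affected. The change is worth making because it is cheap and decides whether the NephroCheck objective gets an interpretable answer.

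**What to change.** In SAP 7.9.1 and Table 13:

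1. Report the AKIRisk rows (risk ratio, TPR, TNR) separately by protocol version at enrolment, using the variable already in Tables 6 and 12. Compute the NC-positive weight within each version.
2. For any pooled estimate, define NC positive in both eras as any score above 0.3 within 2–6 h after T0, on the first or second test. Late-qualifying placebo subjects then count as negative on this factor and keep their weight. This window also fits the protocol's support for the threshold (Section 2.2.1), that "a cutoff of 0.3 yielded good sensitivity and specificity at 4 hours after CPB". Using the first score alone would not do: it would relabel subjects positive on the second 2–6 h test, who were NC positive in both eras.
3. Report the 2–22 h rule only for subjects enrolled under Version 2.0 or later.

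The cost is SAP wording and a few table columns, provided the sampling time of each score is recorded; the documents show that repeat scores may be held but not that their times are. Numbers per version will be smaller, and subjects with no assessable 2–6 h score drop out of the 2–6 h analysis. If the cap closed the observational cohort while randomisation continued, the Version 2.0 figures will need that caveat.
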